2.10. Statistical analyses

2.10.1. Primary analyses

The primary efficacy analysis will test whether income racial/ethnic minority of two to four year old children who are randomized to the NET-Works program have statistically and clinically lower BMI at 24 and 36 months post-randomization relative to usual care comparison group children. Data from all randomized participants will be used to estimate two mixed models. In each, BMI at either 24 or 36 months will be predicted from treatment group (NET-Works, usual care) with age at randomization (2, 3, 4), sex (F, M) and BMI at baseline included as covariates. The NET-Works study is an individually randomized group trial, and dependence may be introduced into the BMI values of NET-Works children whose parents participate in common parenting classes over the course of the three-year intervention while there is unlikely to be dependence in the usual care group where parents are unlikely to ever interact with each other [49]. Among NET-Works children randomized to the intervention group, parenting class cohort will be treated as a random effect, and the intraclass correlation of BMI among children within cohorts will be estimated. Each usual care child will be treated as a random effect and BMI assumed independent. It will be concluded that NET-Works was efficacious if the fixed treatment group parameter in both mixed models is statistically significant and BMI is meaningfully lower (Cohen's $d \geq .30$) among NET-Works children.

Table 2

NET-Works process evaluation.

Fidelity. The extent to which the intervention is delivered as intended; quality of the intervention; how well an intervention is being implemented compared to its original design; could include, but not limited to, content & quality of messages, adherence to protocol, and intervention staff skill/training/certification.

Intervention component	Construct(s)	Data collection method	Completed by	Timing of data collection
Primary care	Content of messages received	Adherence survey	Parent	Baseline, 6, 12, 18, 24, 30 and 36 months
	Provider training attendance and satisfaction	Survey	Pediatric primary care providers	After provider training
Home visits and check-in calls	Content and quality of messages delivered/received	Documentation forms	Intervention staff	After every visit/call
	Staff training attendance, certification and satisfaction	Satisfaction survey	Parent	6, 18, and 30 months
	Content and quality of messages delivered/received	Survey	Intervention staff	After staff training
Parent class sessions and community events	Staff training attendance, certification and satisfaction	Documentation form	Intervention staff	After every class/event
	Content and quality of messages delivered/received	Satisfaction survey	Parent	After every class/event and 6, 18, and 30 months
	Staff training attendance, certification and satisfaction	Survey	Intervention staff	After staff training

Dose delivered. The amount of intervention that was delivered; could include, but not limited to, number and length of sessions implemented.

Intervention component	Construct(s)	Data collection method	Completed by	Timing of data collection
Well-child visit	Attendance	Electronic medical records	Process evaluation staff	Annually
Home visits and check-in calls	Activities completed, messages/materials delivered, attendance	Documentation forms	Intervention staff	After every visit/call
Parent class sessions and community events	Activities completed, messages/materials delivered, attendance	Documentation form	Intervention staff	After every class/event

Dose received. The amount of intervention that was received; could include, but not limited to, participant engagement, and intervention messages or materials received.

Intervention component	Construct(s)	Data collection method	Completed by	Timing of data collection
Well-child visit	Messages/material received	Adherence survey	Parent	Baseline, 6, 12, 18, 24, 30 and 36 months
Home visits and check-in calls	Engagement	Satisfaction survey	Parent	6, 18, and 3 months
Parent class sessions and community events	Engagement	Documentation forms	Intervention staff	After every visit/call

Program design. The assessment of non-specific treatment effects, could include, but not limited to participant satisfaction with, feasibility, and costs of intervention.

Intervention component	Construct(s)	Data collection method	Completed by	Timing of data collection
Well-child visit	Participant satisfaction	Adherence survey	Parent	Baseline, 6, 12, 18, 24, 30 and 36 months
Home visits and check-in calls	Participant satisfaction	Satisfaction survey	Parent	6-, 18-, and 30-month surveys
Parent class sessions and community events	Staff time to prepare and travel for delivery of intervention	Documentation forms	Intervention staff	Quarterly

Reach. The proportion of intended recipients who actually participate in an intervention; the extent to which the intervention is reaching the target population; could include, but not limited to, attendance, participation, and engagement by group (e.g. race, gender, SES, intervention group).

Intervention component	Construct(s)	Data collection method	Completed by	Timing of data collection
Well-child visit	Attendance, participation, and engagement by clinic, race, ethnicity	Similar to above measures, but examined by groups noted in previous column		
Home visits and check-in calls	Attendance, participation, and engagement by race, ethnicity	Similar to above measures, but examined by groups noted in previous column		
Parent class sessions and community events	Attendance, participation, and engagement by location, race, ethnicity	Similar to above measures, but examined by groups noted in previous column		

These analyses will be conducted using multiply imputed datasets. A fully conditional specification approach will be used for the imputation process, and will include in the imputation model all variables included in the primary analytic (scientific) model as well as interactions among them to improve the precision of the imputations. All covariates in the primary

analysis will have been measured at baseline prior to randomization and are therefore available for observed and unobserved BMI values. The random effects estimated in the primary analytic model will also be estimated in the imputation model [50]. The mechanisms that are likely to produce missing observations in the analytic dataset should result in

missing observations that are missing at random (MAR; e.g., early dropouts, busy schedule) or possibly missing not at random (MNAR; e.g., sporadic missing). The primary analytic models will be estimated from imputed datasets that assume all missing observations to be MAR. Sensitivity analyses will assess the severity of non-random missingness that would be necessary to reconsider the conclusions drawn from the primary analysis.

2.10.2. Detectable difference, sample size and power

A power analysis determined the minimum detectable standardized effect size (MDSE, Cohen's d) in BMI for NET-Works versus usual care children at 24 or 36 months post-randomization (i.e., the fixed treatment group parameter). The effective number of follow-up BMI observations was estimated separately for each treatment group by imposing assumptions about the design effect resulting from NET-Works parent-child dyads clustered within parenting class cohorts ($ICC_{PC} = .01\text{--}.03$ NET-Works, $ICC_{PC} = .00$ usual care), the design effect resulting from autocorrelation within cohorts ($r_{PC} = .30\text{--}.50$ NET-Works, $r_{PC} = .00$ usual care) and children ($r_{child} = .40\text{--}.60$) between baseline and follow-up BMI, and the proportion of children from whom BMI will be available (75–85%) (Table 3).

NET-Works dyads will be clustered within about 16 parenting class cohorts ($M = 15.6$ dyads/cohort). The clustered sample size in each treatment group ($n = 250$) was divided by the design effect introduced by clustering within parenting classes, $DEFF_{PC} = [1 + (n - 1)\rho]$, to estimate the effective number of independent dyads in each group. Next, the effective number of independent dyads was divided by the design effect introduced by cohort and child autocorrelation in BMI, $DEFF_{corr} = (1 - r^2)$, to adjust for the efficiency gain resulting from controlling for baseline BMI. In this case, $r = [np/(1 + (n - 1)\rho)]\rho_c + [(1 - \rho)/(1 + (n - 1)\rho)]\rho_s$, where n is the average number of dyads per cluster; ρ is the correlation in BMI values of different children in the same cluster at a single point in time, ICC_{PC} ; ρ_c is the cohort auto-correlation in BMI values, r_{PC} ; and ρ_s is the child auto-correlation in BMI values, r_{child} [51,52]. Finally, the NET-Works and usual care sample sizes were reduced to 75–85% of their estimated values to account for the expected number of children with a follow-up BMI. We will use a generalized Holm procedure to ensure a family-wise Type I error rate of .05 in the two mixed models, so that the treatment group parameter with the smaller p-value will be tested at $\alpha_2 = .025$, while the treatment group parameter with the larger p-value will be tested at $\alpha_2 = .05$ [53,54].

The resulting MDSEs are displayed in Table 2. Given median values for ICC and retention assumptions ($ICC_{PC} = .01\text{--}.03$, $r_{child} = .40$, $r_{PC} = .30$, and 75–85% of randomized children provide follow-up BMI data).

Table 3

Minimum detectable effect size, d , when $\alpha_2 = .025$, $ICC_{PC} = .01\text{--}.03$, $r_{child} = .40$, $r_{PC} = .30$, and 75–85% of randomized children provide follow-up BMI data.

ICC_{PC}	Follow-up BMI data		
	85%	80%	75%
.01	.286	.294	.304
.02	.296	.305	.315
.03	.307	.316	.326

.02, 80% follow-up) and conservative alpha and autocorrelation assumptions ($\alpha_2 = .025$, $r_{PC} = .30$, $r_{child} = .40$), the MDSE is $d = .305$. When $\alpha_2 = .05$, the comparable MDSE is $d = .277$. These effect sizes are in keeping with our stated goal of detecting a clinically meaningful difference ($d = .30$) in BMI between treatment groups at 24 and 36 months.

A similar approach will be utilized for the analysis of secondary endpoints.

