To support full transparency, we have prepared a summary of the adjustments, clarifications and specifications made to statistical analysis plans during the course of this project (section A), followed by the final revised analysis plan (section B). Revisions to the analysis plans approved in April of 2012 are shown as tracked changes. The descriptions address only the primary analysis and, unless relevant to the revised analysis, we have removed from the text below details related to assumptions, power calculations, and secondary and sensitivity analyses. Deletions were not tracked, but the removal of this type of text is denoted by 3 stars (***)�.

The plans shown below were endorsed by the Steering Committee with 5 votes in favor and one abstention. The NHLBI abstained because of concerns about the Vanderbilt change in the primary outcome test. More details on this discussion are shown below in Section 4 and in the addendum.

The preliminary work on the primary analysis done by the COPTR investigators was more extensive than that usually conducted in trials. The construction of simulated data and the implementation of planned analyses exposed details and concerns that otherwise may not have been addressed until after the blind was broken. We are confident that the expanded process of preliminary analyses conducted by the COPTR investigators will expedite the time required to move the COPTR primary outcomes analyses to full publication.

UNIVERSITY OF MINNESOTA

A2: Summary of adjustments, clarifications and specifications

- The primary analysis will not include a random effect for ECFE cohort membership.
At the time the original SAP was approved by the DSMB, it was our intention that consistent and identifiable cohorts of families would attend a series of Early Childhood and Family Education (ECFE) classes together over the duration of the intervention. This component of the NET-Works intervention did not materialize as intended. ECFE participation was lower than expected and there are not identifiable or consistent groups of families that attend these classes.
- The primary analysis will include a random effect for Family Connector (FC) assignment

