It was observed that the home visit component of the NET-Works intervention was delivered to N=257 out of N=265 intervention group families by 7 family connectors. Because it is possible that characteristics of particular FCs may be related to BMI outcomes of the families to which they are assigned, we determined that it would be prudent to model this potential source of dependency in the primary outcome.
The decision to omit the random ECFE term and estimate a random FC term was made after study recruitment was complete and sample size was therefore fixed.
- Family Connector specification
The method for coding the Family Connector was not previously specified. Seven FCs delivered the home visit intervention component to 257 of the 265 treatment group families. Each of these 257 families will be assigned to a FC group based on the primary FC with whom they worked. Treatment group families that did not participate in the home visit intervention component, and all control group families, will be assigned to their own n=1 FC group.
- Multiple imputation specifications
We indicated previously that variables from the analytic model as well as auxiliary variables and interactions would be used in the imputation model. We have now specified a list of 9 candidate auxiliary variables and decided not to include interactions. We also provide more specificity regarding the number of datasets to be imputed (minimum 20) and the principles guiding decisions about the imputation process.

B2: Revised Analysis Plan

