2.4. Primary Analysis

2.4.1. Statistical model and approach

The primary analysis will test whether NET-Works participants have lower BMI at 24 and 36 months relative to comparison participants. We will use data from all randomized participants (intent to treat approach) to estimate two mixed models in which 24 or 36 month BMI values are predicted from randomized treatment group with age group at baseline, sex and BMI at baseline as covariates, and a random intercept for family connector (u_{0j}):

$$\text{BMI}_{ij} = \gamma_{00} + \gamma_{01}\text{NET-Works}_j + \gamma_{20}\text{3yo}_i + \gamma_{30}\text{4yo}_i + \gamma_{40}\text{female}_i + \gamma_{50}\text{BMI baseline}_i + [u_{0j} + e_{ij}].$$

We will conclude that NET-Works was efficacious if the γ_{01} parameter in both mixed models is statistically significant and negative, meaning that BMI is significantly lower among NET-Works children than comparison children.

[figure not shown]
A source of dependence lies in the family connector (FC) assignment. Seven family connectors delivered the home visit component of NET-Works to intervention families. To the extent FC assignments were intended to be culture-specific, and FCs may vary slightly in their manner of delivering intervention content to the families with whom they work, dependence may be introduced through common FC assignment. As such, it will be important to account for dependence in BMI introduced through FC assignment.

Each of the families will be assigned to a FC group based on the primary FC with whom they worked. Treatment group families that did not participate in the home visit intervention component, and all control group families, will be assigned to their own n=1 FC group following the method of Esserman et al. (2012).

2.4.3. Missing data including level of attrition, loss to follow-up, and missing data treatment

The primary analysis will be conducted using multiply imputed data. We plan to use fully conditional specification to impute sporadically missing followed by 12, 24 and 36 month monotonically missing BMI values. We anticipate imputing a minimum of 20 datasets based on the observed missingness to date in post-baseline BMI values but may upwardly adjust this number to ensure adequate power (Graham et al., 2007). The imputation model will include the

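### The stated detectable effects (Table 3, d = .305) assume 16 parenting-class cohorts; the revised primary model clusters on 7 family connectors and shows no figure for that structure

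*Protocol*

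**What the plan says.** The Protocol joins two texts: the revised primary analysis plan (sections A2 and B2) and the published design paper.

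**Design paper, 2.10.2.** The detectable-effect calculation rests on this structure: "NET-Works dyads will be clustered within about 16 parenting class cohorts", mean 15.6 dyads, 250 per arm, and no clustering under usual care. At ICC .02, 80% follow-up, alpha .025 and autocorrelations of .30 (cohort) and .40 (child), it reports d = .305. At alpha .05 it reports .277. It concludes: "These effect sizes are in keeping with our stated goal of detecting a clinically meaningful difference", namely d = .30.

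**A2.** The class-cohort term is withdrawn: "The primary analysis will not include a random effect for ECFE cohort membership". The stated reason is that stable class groups never formed. A connector effect replaces it: "Seven FCs delivered the home visit intervention component to 257 of the 265 treatment group families". Intervention families without home visits "and all control group families, will be assigned to their own n=1 FC group". On timing: "The decision to omit the random ECFE term and estimate a random FC term was made after study recruitment was complete", when the sample size was already fixed.

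**B2, 2.4.1.** The current primary model carries "a random intercept for family connector" and no class-cohort term.

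**Introductory text to the revised plans.** It says that, "unless relevant to the revised analysis, we have removed from the text below details related to assumptions, power calculations" and some other material.

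**The concern.** Replacing about 16 clusters of 15.6 with 7 clusters of about 36.7 raises the design effect at any given positive ICC, and it leaves far fewer clusters from which to estimate the between-cluster variance. Yet every detectable-effect figure in the document, and the sentence tying those figures to the d = .30 goal, describes the structure that was abandoned. Nothing tells the reader that Table 3 predates the model now specified.

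The stake is interpretation. B2 declares efficacy only if both the 24- and the 36-month models are significant. A non-significant result at either visit would naturally be read against .305, which does not belong to the model being fitted.

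**Working it through.** **Inputs from the documents**
- Original structure: 250 per arm, 15.6 dyads per cohort.
- Revised structure: 257 families in 7 groups (257/7 = 36.71) plus 8 intervention singletons (265 − 257).
- ICC .01–.03; autocorrelations .30 (cohort) and .40 (child), the plan's conservative values; alpha .025; follow-up 75–85%.

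**Assumptions**
- 80% power, which is not stated but reproduces the table.
- 265 controls.
- The class-cohort ICC range and the .30 cluster autocorrelation carried over to connectors.
- Equal caseloads; unequal ones would raise the detectable effect further.

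**Formulas (2.10.2)**, with m the cluster size:
- DEFF = 1 + (m − 1)·ICC
- r = [m·ICC/DEFF]·.30 + [(1 − ICC)/DEFF]·.40
- Effective n = N/DEFF/(1 − r²) × follow-up; for singletons and controls, N/(1 − .40²) × follow-up
- MDSE = (two-sided critical value + 80% power quantile) × √(1/n₁ + 1/n₀)

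**Step 1: reproduce the plan (ICC .02, 80% follow-up)**
- DEFF = 1 + 14.6 × .02 = 1.292
- r = .3759
- n₁ = 250/1.292/(1 − .3759²) × .8 = 180.3
- n₀ = 250/.84 × .8 = 238.1
- MDSE = .3044 (normal) or .3053 (t, about 400 df); stated .305
- At alpha .05: .277; stated .277

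All nine cells of Table 3 reproduce to within .001 with the t quantiles.

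**Step 2: same method, connector structure (ICC .02, 80% follow-up)**
- DEFF = 1 + 35.71 × .02 = 1.714
- r = .3572
- Clustered: 257/1.714/(1 − .3572²) × .8 = 137.5
- Singletons: 8/.84 × .8 = 7.6, so n₁ = 145.1
- n₀ = 265/.84 × .8 = 252.4
- SE = √(1/145.1 + 1/252.4) = .1042
- MDSE = .321 (normal) or .322 (large-df t)
- Power at d = .305: Φ(.305/.1042 − 2.241) = .754

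**Step 3: all cells.** Large-df t; the third decimal can move by .001 with the df chosen.

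| Assumed connector ICC | 85%: stated → revised | 80%: stated → revised | 75%: stated → revised | Power at .305 (80% follow-up) |
|---|---|---|---|---|
| .01 | .286 → .291 | .294 → .300 | .304 → .310 | 82% |
| .02 | .296 → .312 | .305 → .322 | .315 → .333 | 75% |
| .03 | .307 → .332 | .316 → .343 | .326 → .354 | 70% |

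Every cell worsens, although the enrolled intervention arm (265) exceeds the planned 250.

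**Step 4: sensitivity (ICC .02, 80% follow-up unless stated)**
- Alpha .05: .293 against .277.
- Controls: .326 with 250, .330 with 235.
- 250 per arm, of whom 242 clustered and 8 singletons in the intervention arm: .329.
- Autocorrelations .40/.50: .306 against .289 for the old clustering. At .50/.60: .284 against .268.
- Connector ICC at which .305 is just met: about .012 with 265 per arm, about .009 with 250 per arm.
- Small-sample df (no df method is stated). A Satterthwaite-type approximation with A = 1/145.1 and B = 1/252.4 gives (A + B)²/(A²/6 + B²/211) = 14.7 df and MDSE .350. The 16-cohort design on the same basis has 44.4 df and .313. Over ICC .01/.02/.03 the pairs are .321/.350/.377 against .301/.313/.324.

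**The case against.** The strongest reply is that nothing is miscalculated. Section 2.10.2 belongs to a design paper published while recruitment was under way, and its power text matches the model in that same paper. The connector model is a later, openly declared revision. The introduction says that power details were taken out of the revised text, and gaps in the section numbering of B2 are consistent with an extract, so a recalculation may exist. The sample size was fixed, so no design decision hangs on the answer. The connector ICC appears nowhere: the .01–.03 range was chosen for families sharing group classes, whereas connectors work one-on-one. The headline power figures also use the least favourable autocorrelations, and the small-df result depends on a method the plan does not name.

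Much of this stands. The claim can only be that no figure is shown, not that none was calculated. The size is conditional on an assumed ICC, and the break-even of about .012 lies inside the borrowed range. The df results are a sensitivity analysis only.

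It does not remove the point. The removal of power text excepted what is relevant to the revised analysis, and a new cluster structure makes the detectable effect relevant. The autocorrelations used here are those behind the plan's own headline figure, so like is compared with like. B2 itself gives reasons to expect connector dependence: culture-specific assignment and variation in delivery. Both texts are presented together as the protocol, with nothing limiting Table 3 to the earlier design.

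**Conclusion.** The concern holds. The stated detectable effects are right for 16 class cohorts and do not describe the current primary model, for which neither a detectable effect nor a connector ICC is shown.

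On the plan's own method, with its ICC range carried over to connectors, the central figure moves from .305 to .322, about 5% larger (.322/.305 = 1.056). Power at d = .305 falls from 80% to about 75%, and to about 70% at ICC .03. At ICC .01 the result is .300 and the d = .30 goal is still just met. More favourable autocorrelations also bring the ICC .02 figure back to about .305 or below; few-cluster df push it up to about .350.

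This should be fixed, but it is a matter of reporting and interpretation. It does not affect the validity of the test or the fixed sample size.

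**What to change.** - Add to B2 a short table of minimum detectable effects for the connector-clustered model. It should state the actual connector caseloads, the 8 intervention singletons, the observed control n, a connector ICC range with its justification, the power level, and the df method for a model with seven multi-family clusters. If such a recalculation already exists, include it or point to it.
- Keep Table 3 as the record of the original design, and say in B2 that it refers to the 16-cohort structure.
- Qualify the statement that the effect sizes agree with the d = .30 goal so that it covers the 16-cohort design only. As the design paper is published, a note in B2 is enough.

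The cost is one small table and one qualifying sentence, best added before unmasking. No extra enrolment and no change to the model, alpha or success rule is needed. The stated sensitivity becomes modestly less favourable.
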